Sample size. A power analysis to determine the needed sample size for this study resulted in us having to recruit a minimum of N=120 (40 in each condition) to achieve a balanced factorial design, which should be quite attainable given the interest indicated by the resident directors. Assuming 25% attrition, our recruitment plan will yield 90 participants, which will allow us to assess changes in performance as a function of training. Given the number of primary comparisons (3 scores of cognitive control at 2 time points (Pre- and Post-training)), there would be 95% power to reveal a group X session interaction on any given outcome, even with only 90 total participants split across the 3 groups. This corresponds to a medium effect size of .53, which is reasonable for a feasibility study of this size given the study-associated logistics. Pre- and post-training outcome data will be modeled using mixed within- and between-subjects GLMs and multivariate regressions¹⁰⁹. Significant interactions will be interrogated with appropriate follow-up tests between each group, including the direct assessment of effect size comparisons calculated using Satterthwaite's approximation¹¹⁰.

[figure not shown]
The goal of this R21 is to test the feasibility of deploying a targeted digital health remediation program for older adults in senior living communities based upon an initial characterization of these abilities. Below we discuss the logistics towards realizing this goal.

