Mixed Model Approach. Here we propose to use a sequential exploratory mixed method design¹¹⁵⁻¹¹⁹ for this pilot study. Specifically, a quantitative design will be used to: (1) collect descriptive information regarding older adults' perceptions of each app to enhance the UX experience for this particular population to explore the feasibility of self-administration for cognitive assessment and remediation, and (2) make pre-, post-, within- and across-group comparisons of cognitive functioning based on neurocognitive test performance and self-rated assessments. The qualitative approach will begin with local semi-structured interviews regarding the use of each app, first in a group of 10 one-on-one sessions with seniors led by our UX testing consultant (see **Letter of Support**), followed by subsequent interrogation by senior-centric UX group testing group (Longevity Explorers™, see **Letter of Support**) whose members are seniors trained in UX design refinement. Using data gathered from these experiences, we will augment the UX design of each app for subsequent dissemination to the Brookdale Senior Centers for use. Brookdale participants will be asked questions about their experience following training, with feasibility of program participation assessed quantitatively by measuring the number and percentage of sessions completed per participant. Questions at this time point (previously used by Hill and colleagues⁹⁰) will include "Do you feel your everyday thinking abilities have changed from doing the computer exercises and, if so, how? 2. What did you like about doing the computer exercises? 3. What did you dislike about doing the computer exercises? 4. Now that the study is over, would you keep doing the computer exercises?" Responses during said interviews will be transcribed, with frequency tallies of response consistencies per question across participants being tabulated. We will perform thematic analyses for the identification of important patterns/themes⁹⁰, creating a coding framework that maximizes coherence amongst categories emerging from the qualitative data¹²⁰⁻¹²².

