Protocol. Following the initial local UX testing, a convenience sample of 120 older adults will be recruited from throughout the Brookdale Senior Centers throughout the United States (see **Figure 3**; see **Recruitment and Retention Plan** for additional participant enrollment details). These individuals will be asked to complete the battery of tasks on the ACE platform (~45min) to characterize cognitive control abilities before and after the assigned intervention. Following their initial assessment, each participant will be randomly assigned (using a pseudo-randomized blocked design using blocks of 9 to ensure equivalent representation across groups) to a one of three intervention types: directed training (DT) on the ACCT platform, non-directed training (nDT) on the ACCT platform, or an expectancy-matched placebo control platform (PC). We will ask each resident director and their residents to refrain from discussing their assigned intervention with other communities to preserve blinding across sites. The total training experience will encompass 6 weeks of training (3 days/week), with each training session lasting 36 minutes (not including self-paced breaks). Each participant in the DT and nDT groups will engage in 12 3-minute blocks of submodules in each training session on the ACCT platform. However, those in the nDT group will play each of the three submodules 4 times equally, while participants in the DT group will play 12 blocks proportionally weighted towards the cognitive control domain(s) that are most deficient at baseline as determined by their baseline ACE performance, and thus most likely to benefit from directed training. For example, if (following the ACE assessment) a given individual shows deficiencies on their attention and working memory scores but normal performance in their goal-management abilities, they will be prescribed 5 training runs of the attention & working memory modules and only 2 of the goal management module. Customization of each DT participant regime will be accomplished via a web portal at UCSF that transmits personalized training parameters directly to the individual's ACCT application. Each training program contains self-guided instructional videos and practice modules for each treatment, consisting of 6 weeks of training (3 days per week). Training sessions are linked, such that the next session begins at the level attained at the end of the previous session. Participants are provided two types of feedback: 1) real-time feedback – indicating whether the participant successfully detected or classified the target and 2) punctuated feedback – participants advance through a series of “levels” that are reported at the beginning and end of each run. We will provide weekly feedback about intervention use and performance improvement (in addition to daily in-app feedback), in support of its utility found in a recent survey¹²³: 79% of health app users indicated that periodic feedback about their app usage encouraged them to continue.

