
```

graph TD
    A["Pseudo-randomize individuals participants (9 per block design)"] --> B["DT"]
    A --> C["nDT"]
    A --> D["PC"]
    B --> E["ACE & Surveys  
Baseline"]
    C --> E
    D --> E
    E --> F["6 week of training"]
    F --> G["ACE & Surveys  
Follow-up"]
    G --> H["ACE & Surveys"]
    style A fill:#e0e0e0,stroke:#000,stroke-width:1px
    style B fill:#fff,stroke:#000,stroke-width:1px
    style C fill:#fff,stroke:#000,stroke-width:1px
    style D fill:#fff,stroke:#000,stroke-width:1px
    style E fill:#fff,stroke:#000,stroke-width:1px
    style F fill:#fff,stroke:#000,stroke-width:1px
    style G fill:#fff,stroke:#000,stroke-width:1px
    style H fill:#fff,stroke:#000,stroke-width:1px
    
```

Expectancy-Matched Placebo Control. The placebo control group (PC) will engage in a battery of three apps delivered in the same prescribed manner as the other two groups, which we hypothesize as based on our experience will have minimal positive impact on the cognitive abilities we are assessing: i) an app with 100 different logic games of varying difficulty and length, ii) a language-learning app with 10 language options, and iii) an app that offers a guided Tai Chi program. The total training experience here will also be for 6 weeks (3 days/week), with each training session lasting ~30 minutes where participants will be asked to use each of the submodules for 10 minutes (not including self-paced breaks). We have already determined that this approach generates matched expectancy of benefits compared to our training groups by questioning 100 naïve individuals to predict their expected improvement on each cognitive domain after training on these apps (see ¹²⁴ for details of expectancy testing). This revealed that placebo training generates equivalent expectations of improvement across each outcome measure as the DT group, thus serving as an effective placebo condition. Furthermore, initial pilot work examining transfer effects following training on this battery has shown no evidence of improved cognitive control with respect to attention or working memory abilities, supporting its utility as a placebo control.

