Assessments. All OAs will complete assessments at two periods: baseline and immediately following the intervention. In addition to measuring transfer to benefits to cognitive control (using ACE), we will also assess transfer of gains to functionally-relevant outcome measures, notably the Everyday Cognition Scale (ECog) to assess their ability to perform everyday tasks that demand memory, language, visuospatial abilities, planning, organization, and divided attention^{125,126}. The ECog scale has been used in other cognitive interventions trials and proven to be sensitive enough to detect improvements in healthy OAs and differentiate OAs from mild MCI^{127,128}. This survey will be sent directly to participants via an automated email campaign from Qualtrics™, with help from local resident mentors to complete these surveys on the same devices. Other surveys sent through this mechanism will include: i) a customized survey assessing participant expectancy across groups to further explore possible uncontrolled placebo effects (see for a description of this approach), ii) distractibility (via the Cognitive Failures Questionnaire)¹²⁹, and general health and well-being (SF-36)¹³⁰.

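### Follow-up ACE and surveys are tied to the end of training, with no provision for participants who stop or lag, so the limited-efficacy estimate may describe only those who stay

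*Combined protocol and SAP*

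**What the plan says.** The Assessments section sets the outcome schedule in one sentence: "All OAs will complete assessments at two periods: baseline and immediately following the intervention". This covers ACE and the questionnaires (ECog, Cognitive Failures Questionnaire, SF-36 and an expectancy survey), which go out by automated email. The Protocol section agrees, with ACE given "to characterize cognitive control abilities before and after the assigned intervention". Neither section names a study day or week, a visit window, or what happens to a participant who stops training or lags.

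The Protocol and Expectancy-Matched Placebo Control sections give all three arms the same nominal course, 6 weeks at 3 days a week. Less than full training is foreseen: the Mixed Model Approach section has "feasibility of program participation assessed quantitatively by measuring the number and percentage of sessions completed per participant".

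The Sample size section states: "Assuming 25% attrition, our recruitment plan will yield 90 participants, which will allow us to assess changes in performance as a function of training". It names GLMs and regressions on the pre- and post-training data, but no analysis set and no method for missing outcomes. The fourth of the four feasibility markers under Markers of success is limited-efficacy testing of the two ACCT versions, and the pilot is meant to prepare an R01 application.

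On the order of events, the Protocol section says "Following their initial assessment, each participant will be randomly assigned". The flow diagram, as extracted, draws randomization and the three arms ahead of the baseline assessment, and shows one more assessment box after follow-up.

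**The concern.** If the outcome visit is defined by the end of training, someone who abandons training in week 2 has no clearly defined visit. The natural default is that this person supplies no follow-up ACE or survey and is counted within the 25%. The arms are then compared among those who stayed.

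That comparison is not protected by randomization, and the arms differ in ways that could affect who stays. DT concentrates on each resident's weakest domains, nDT spreads blocks evenly, and placebo uses three unrelated apps for about 30 minutes a session against 36. A responsiveness estimate from those who stay could mislead the planning of the R01. The stake is confined to the fourth marker. Acceptability, enrollment and drop-out counts, and data quality do not rest on the ACE effect, although data quality would record the missing follow-ups.

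Much of the loss may be avoidable. The surveys arrive by email and ACE runs on the resident's device, so neither requires that the person is still training.

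**Working it through.** **1. The texts side by side.** Assessments and Protocol anchor follow-up to the intervention. Mixed Model Approach expects fewer sessions than the full 6 × 3 = 18 in some participants. Sample size plans the change analysis on fewer people than are randomized. No section links these by saying whether a person with few sessions is still assessed, or when.

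**2. The plan's own figures.** 120 × (1 − 0.25) = 90, so 30 of 120 are planned to be unavailable, leaving 90 / 3 = 30 per arm. The 90 reproduces exactly.

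The stated 95% power at effect size .53 reproduces only with inputs that the plan does not give. Assume that .53 is the standardized distance between the extreme groups of three equally spaced means, so f = .53/√6 = 0.216. Assume also alpha 0.05 and a pre-post correlation of 0.5. For the group × session interaction, λ = f² × N × 2/(1 − ρ) with 2 and 87 degrees of freedom, and power is 0.960. Other readings give other values; for example, a pairwise comparison at .53 with 30 per arm has power 0.537.

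**3. Completers against all randomized (illustration).** Assume that the whole 25% stop training, that completers show .53 as a standardized difference, and that stoppers keep a fraction s of it. The effect in all randomized is .53 × (0.75 + 0.25s).

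| s | All-randomized effect | Excess of .53 over it |
|---|---|---|
| 0 | .53 × 0.750 = 0.398 | 33% |
| 0.5 | .53 × 0.875 = 0.464 | 14% |
| 1 | .53 × 1.000 = 0.530 | 0% |

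The excess is 1/(0.75 + 0.25s) − 1, so it does not depend on the value .53.

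**4. Unequal stopping (illustration).** Suppose that stayers differ from stoppers by δ SD whatever their treatment. With a proportion p stopping, the stayers' mean differs from the arm's mean by pδ, so the contrast between two arms is shifted by (p₁ − p₂)δ. With 30% against 20% and δ = 0.3, the shift is 0.10 × 0.3 = 0.03. With 35% against 15% and δ = 0.5, it is 0.20 × 0.5 = 0.10. All of these inputs are assumptions, and the sign could go either way.

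**5. Power if everyone is assessed.** Using the variant from step 2 and the effects from step 3:

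| s | All 120 assessed | Only 90 assessed, same effect |
|---|---|---|
| 0 | 0.892 | 0.778 |
| 0.5 | 0.965 | 0.895 |
| 1 | 0.991 | 0.960 |

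Against the completer analysis (0.960 at .53 with 90), assessing all 120 costs about 7 points at worst and gains about 3 at best. The 120 is an upper limit, because some people will leave the study.

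**6. Timing for those who lag.** If training ran until session 18, follow-up would fall at 18/3 = week 6, 18/2 = week 9 or 18/1.5 = week 12 for 3, 2 or 1.5 sessions a week. If training ends at calendar week 6, it falls near week 6 for everyone. The documents do not say which applies.

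**The case against.** The best defense is that the plan describes a 6-week program in every arm and that the Assessments section covers all participants. If the intervention is a calendar period, a person who stops in week 2 still has an end of period, and follow-up already falls near week 6. Counting the percentage of sessions completed fits that reading at least as well as training until session 18. Sessions are linked, but only the breaks are called self-paced. A reader might infer that slow finishers are tested later, or that early stoppers are excluded from follow-up. Neither is established: assessing stoppers is neither planned nor ruled out. The Protocol section also refers to a Recruitment and Retention Plan that is not among the documents.

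Nor does the Sample size section define its 25% as stopping training. Sessions completed, drop-out and missing data are already to be recorded, so part of the separate reporting is in place.

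All of this stands, and it limits the point to what is undefined. It does not remove it. A statement that all will be assessed cannot settle the matter when another section bases the analysis of change on 90 of 120 and no section provides for assessing those who stop.

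A reader might also infer from the diagram that allocation precedes baseline. The Protocol text says the opposite explicitly, and the extracted figure may be unreliable, so this is only a point to reconcile.

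**Conclusion.** The concern holds in a limited form. The only post-baseline assessment is anchored to the end of the intervention, nothing provides for participants who stop or lag, and the assessment of change rests on those remaining after 25% attrition. The responsiveness estimate may therefore describe only those who stay.

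The illustrative size is an all-randomized effect of .40 to .53, with the completer figure 0% to 33% too high. This rests on three assumptions: .53 is a standardized difference, it is the effect in completers, and the whole 25% are people who stop training. The 33% is the bound at which stoppers gain nothing. It should not be read as an estimate of bias in this trial, and the documents do not show that the completer figure must be too favorable.

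This is an advisable change to one secondary use of a feasibility pilot. It does not undermine the pilot's primary aim.

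**What to change.** In the Assessments section, set the follow-up ACE and surveys in a short fixed window about 6 weeks after randomization, for every randomized participant regardless of sessions completed. This takes training to start directly after randomization. Dating the window from randomization also gives a visit to anyone who never starts. Align the Protocol wording with it.

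Send the existing email and app prompts to those who have stopped. In the Sample size section, state that all who provide data are analyzed in the arm to which they were randomized. Under Markers of success, report stopping training and having no follow-up outcome as two separate counts.

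The cost is protocol wording and a calendar trigger in tools already planned: automated survey emails, the tracking portal and onsite help from resident directors. The downsides are extra reminders and some lagging participants tested before their last session. The change recovers people who stop training but remain reachable, not those who leave the study.

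Separately, and allowing for extraction error, check the flow diagram against the Protocol and Assessments sections on the order of randomization and baseline and on the number of assessments, and correct whichever is wrong.
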